5.5 General Concomitant Medication and Supportive Care Guidelines

Antiviral, antifungal and antibacterial prophylaxis and monitoring should follow institutional practice as per the BMT-SOP. These typically include: daily acyclovir (or equivalent) for HSV prophylaxis, bactrim (or equivalent) for PCP prophylaxis, IV gammaglobulin for hypo-gammaglobulinemia, and azole (with mold activity) use for fungal prophylaxis as well as monitoring of beta-glucan and galactomannan levels. Growth factor support (e.g. GCSF, erythropoietin) and transfusion support is allowed, and can be used at the discretion of the investigators.

5.6 Duration of Therapy

Duration of therapy will depend on individual response, evidence of disease progression, and tolerance. In the absence of treatment delays due to adverse events,

CONFIDENTIAL

This document is confidential. Do not disclose or use except as authorized.

treatment (including induction followed by maintenance therapy) may continue for 60 weeks or until one of the following criteria applies:

- Disease progression (as defined in **Appendices E-F**). As T-cell infiltration of the tumor site (e.g. granulocytic sarcoma, skin) can look like progressive disease, please discuss the results of clinical or radiographic assessments (e.g. leukemia cutis site inflammation; granulocytic sarcoma scans) showing progressive disease with the study PI before removing a patient from the study for disease progression. Patients with radiographic progression who are deriving clinical benefit will be allowed to remain on treatment until the next schedule efficacy assessment.
- Intercurrent illness that prevents further administration of treatment,
- Unacceptable adverse event(s), requiring temporary or permanent stopping of Ipilimumab defined in **Section 6.1.3**
- Participant decides to withdraw from the study, or
- General or specific changes in the participant's condition render the participant unacceptable for further treatment in the opinion of the treating investigator

5.7 Criteria for Taking a Participant Off Protocol Therapy

Participants will be removed from study when any of the criteria listed in Section 5.7 apply. The reason for study removal and the date the participant was removed must be documented in the study-specific case report form (CRF). Alternative care options will be discussed with the participant.

Patients will be removed from the study for any of the following reasons:

- Death
- Adverse event(s) that, in the judgment of the investigator, may cause severe or permanent harm or which rule out continuation of study drug
- General or specific changes in the patient's condition render the patient unacceptable for further treatment in the judgment of the investigator
- Suspected pregnancy
- Lost to follow-up
- Patient withdraws consent
- Investigator removes the patient from study
- Dana Farber Cancer Institute decides to close the study

The reason for taking a participant off study, and the date the participant was removed, must be documented in the case report form (CRF). In addition, the study team will ensure Off Treatment/Off Study information is updated in OnCore in accordance with DF/HCC policy REGIST-101.

In the event of unusual or life-threatening complications, participating investigators must immediately notify the Principal Investigator.

**[name] MBBS DPhil,
Ph: [contact]
Pager: [name]**

CONFIDENTIAL

This document is confidential. Do not disclose or use except as authorized.

5.8 Duration of Follow Up

Participants removed from treatment for unacceptable AEs will be tracked for 30 days from last study treatment to document AE outcome (resolution, improvement, persistence or progression). For all patients, data on survival, disease status (remission/progression/relapse), and alternative therapies (if any) will be tracked for 1 year after completion of last study treatment.

Participants will also be asked to allow for long-term follow up so that survival, relapse and late toxicities, should they occur beyond 1 year, may also be identified. Long-term follow up will be at DFCI if participants live locally or with their local oncology providers if they live remotely. For participants living remotely, phone calls to their local oncology providers may be made on a 6-month basis.

5.9 End of Study Definition.

The end of study is defined as any one of the following (whichever occurs first):

- The date of the 1-year follow-up
- The date of death
- Lost to follow-up
- Patient withdraws consent

6. DOSING DELAYS/DOSE MODIFICATIONS

Dose delays and modifications during the study therapy will be made using the following recommendations. Toxicity assessments will be done using the CTEP Version 5.0 of the NCI Common Terminology Criteria for Adverse Events (CTCAE) which is identified and located on the CTEP website at:

http://ctep.cancer.gov/protocolDevelopment/electronic_applications/ctc.htm.

If possible, symptoms should be managed symptomatically. In the case of toxicity, appropriate medical treatment should be used (including anti-emetics, anti-diarrheals, etc.).

All CTCAE grade 3 and higher events experienced by participants will be collected from the time of the first dose of study treatment, through the study and until the final study visit. Participants continuing to experience toxicity at the off study visit may be contacted for additional assessments until the toxicity has resolved or is deemed irreversible.

6.1 Anticipated Toxicities

A list of the adverse events and potential risks associated with the agents administered in this study appear below and will determine whether dose delays and modifications will be made or whether the event requires expedited reporting in addition to routine reporting.

CONFIDENTIAL

This document is confidential. Do not disclose or use except as authorized.

6.1.1 Adverse Event List for CD25/Treg-depleted DLI

Unselected DLI for treatment of malignant disease relapse has been associated with Teff-mediated GVHD flare, and with myelosuppression primarily in cases of significant leukemia/lymphoma involving the bone marrow (owing to replacement of host hematopoiesis). However, infusion of the donor CD25/Treg-depleted cells was found to be safe in our phase I clinical trial. All patients will be closely monitored for any adverse effects including GVHD and marrow suppression.

- **GVHD**

The severity of acute GVHD is measured according to the extent of involvement of each of the three organs: skin, liver, and GI tract. The current grading system for acute GVHD ranges from grade 0 (no GVHD) to grade IV (severe, life threatening), and is shown in Appendix 1. Details on the management of acute GVHD will be discussed in **Section 6.1.7**

- **Pancytopenia**

Myelosuppression can be seen after DLI and may be pronounced in patients with active disease in the bone marrow at the time of DLI. The management of pancytopenia is outlined in **Section 6.1.8**

6.1.2 Adverse Event List for Ipilimumab

Ipilimumab can result in severe and fatal immune-mediated adverse events probably due to T-cell activation and proliferation. A listing is provided in **Section 7.2.1.2**. These can include (but are not limited to) autoimmune hemolytic anemia, acquired anti-factor VIII immune response, autoimmune aseptic meningitis, autoimmune hepatitis, autoimmune thyroiditis, hepatic failure, pure red cell aplasia, pancreatitis, ulcerative and hemorrhagic colitis, endocrine disorders (e.g., autoimmune thyroiditis, hyperthyroidism, hypothyroidism, autoimmune hypophysitis/hypopituitarism, and adrenal insufficiency), ocular manifestations (e.g., uveitis, iritis, conjunctivitis, blepharitis, and episcleritis), sarcoid granuloma, myasthenia gravis, polymyositis, and Guillain-Barre syndrome. The majority of these reactions manifested early during treatment; however, a minority occurred weeks to months after discontinuation of Ipilimumab especially with the initiation of additional treatments.

6.1.3 Ipilimumab Dose Modifications/delays

Intra-patient dose modifications of Ipilimumab are not allowed in this study as lower doses have not been found to be less likely to lead to resolution of immune-related AEs that were seen at higher doses.

Decisions to delay an Ipilimumab dose will be made based on specified safety criteria. Treatment with Ipilimumab will be delayed or discontinued if the subject experiences at least one adverse event, specified below, considered by the

CONFIDENTIAL

This document is confidential. Do not disclose or use except as authorized.

investigator to meet the criteria as outlined. The investigator should contact the Protocol Chair for any adverse event that will prompt a delayed dose or discontinuation of Ipilimumab. The following criteria will be used to determine dose delays, restarting doses, or discontinuing Ipilimumab:

It is necessary to delay study drug dosing for the following related adverse event(s):

- Any \geq Grade 2 non-skin related adverse event (including irAEs), except for asymptomatic laboratory abnormalities
- Any \geq Grade 3 laboratory abnormality
- Any adverse event, laboratory abnormality or intercurrent illness that, in the judgment of the investigator, presents a substantial clinical risk to the subject with continued dosing
- Any \geq Grade 3 skin related adverse event regardless of causality

Restart Ipilimumab dosing if/when the adverse event(s) resolve(s) to \leq Grade 1 severity or return to baseline within 3 weeks of initiating the dose delay (no more than 6 weeks since the most recent prior dose administration).

The maximum amount of time that induction Ipilimumab can be delayed due to adverse events before patients must be taken off treatment is 3 weeks, (i.e. 6 weeks between doses, respectively). Patients on maintenance Ipilimumab dosing must be taken off treatment if dosing is delayed for more than 4 weeks due to toxicity.

In the event of a dose delay:

- Certain study assessments, including bone marrow biopsy, T-cell chimerism, tumor measurement (CT or PET/CT), and/or correlative study samples associated with day 1 of the delayed cycle may be assessed on the original planned cycle day 1 (first day of dose delay) only (do not need to be re-assessed on actual cycle day 1, the day of cells and Ipilimumab infusion)
- In the event of a dose delay of the first dose (cycle 1, day 1) baseline bone marrow biopsy, radiographic assessment, T-cell chimerism do not need to be reassessed, even if those tests fall outside the required baseline time frames.
- If Ipilimumab dosing must be delayed for > 3 weeks (more than 6 weeks since the prior dose administration) for any of the above reasons, patients must come off treatment, except after approval by the study chair for individual cases with ongoing clinical benefit.

CONFIDENTIAL

This document is confidential. Do not disclose or use except as authorized.

6.1.4 Ipilimumab Discontinuation

Criteria that Require Permanent Discontinuation of Ipilimumab:

Subjects MUST discontinue study treatment for any of the following reasons that are not related to a related adverse event:

- Withdrawal of informed consent (subject's decision to withdraw for any reason)
- Pregnancy
- Termination of the study
- Loss of ability to freely provide consent through imprisonment or involuntary incarceration for treatment of either a psychiatric or physical (e.g., infectious disease) illness.

Subjects must permanently discontinue Ipilimumab if they experience any adverse event, laboratory abnormality or intercurrent illness that, in the judgment of the investigator, presents a substantial clinical risk to the subject with continued dosing.

The following neurological adverse events require permanent discontinuation of Ipilimumab and defines unacceptable neurotoxicity:

- Any neurologic motor toxicity \geq Grade 3 regardless of causality
- Any \geq Grade 3 treatment-related sensory neurologic toxicity

Ipilimumab need NOT be discontinued in the following situations:

- Potentially reversible inflammation ($<$ Grade 4), attributable to a local antitumor reaction and a potential therapeutic response
- Subjects with the following conditions where in the investigator's opinion continuing study drug administration is justified
- Ocular toxicity that has responded to topical therapy
- Endocrinopathies where clinical symptoms are controlled with appropriate hormone replacement therapy.

Note: Ipilimumab may not be restarted while the subject is being treated with systemic corticosteroids except for subjects on stable doses of hormone replacement therapy such as hydrocortisone for adrenal insufficiency.

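### For treatment-related events, Sections 6.1.3 and 6.1.4 attach different mandatory actions to one trigger: delay with restart, or permanent discontinuation

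*Combined protocol and SAP*

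**What the plan says.** Section 6.1.3 (Ipilimumab Dose Modifications/delays) speaks of treatment being delayed or discontinued and announces its rules with "The following criteria will be used to determine dose delays, restarting doses, or discontinuing Ipilimumab". The list that follows opens "It is necessary to delay study drug dosing for the following related adverse event(s". Its third item is "Any adverse event, laboratory abnormality or intercurrent illness that, in the judgment of the investigator, presents a substantial clinical risk to the subject" if dosing continues. The next instruction begins "Restart Ipilimumab dosing if/when the adverse event(s) resolve(s) to" Grade 1 or lower, or to baseline, within 3 weeks of the start of the delay and no more than 6 weeks after the previous dose.

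Section 6.1.4 (Ipilimumab Discontinuation) says "Subjects must permanently discontinue Ipilimumab if they experience any adverse event, laboratory abnormality or intercurrent illness that, in the judgment of the investigator, presents" that same risk. It then lists a few situations in which stopping is not required: local inflammation from an antitumor reaction, ocular toxicity that has responded to topical treatment, and endocrinopathy controlled by hormone replacement.

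Section 5.6 (Duration of Therapy) lets treatment run until any one of several criteria applies. One of them is "Unacceptable adverse event(s), requiring temporary or permanent stopping of Ipilimumab defined in" Section 6.1.3. Section 5.3.1 states that dose delays are permitted.

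**The concern.** The trigger is a catch-all. It governs toxicities that the organ-specific rules of Section 6.1.13 do not name, in a combination where Section 13.4 already reports a fatal dose-limiting toxicity (DLT) at dose level 2 and late serious events at dose level 1. Whether a patient judged to be at substantial risk receives ipilimumab again should have one answer in the protocol. Here an investigator who follows 6.1.3 may restart after resolution, and one who follows 6.1.4 may not.

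The data are affected as well. The number of ipilimumab doses a patient receives feeds the response-evaluable definition in Section 11, so membership of that set can turn on an unstated choice between two sections.

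**Working it through.** The plan gives no figure to reproduce. The check is a comparison of text, followed by a short count from the dosing calendar.

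**Step 1: the trigger.** In both sections the condition ends "laboratory abnormality or intercurrent illness that, in the judgment of the investigator, presents a substantial clinical risk to the subject with continued dosing", and in both it begins with any adverse event. The two conditions are the same words.

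**Step 2: scope and action.**

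| | 6.1.3 | 6.1.4 |
|---|---|---|
| Causality | List headed as related events | No limit |
| Action | Delay is necessary | Permanent discontinuation is mandatory |
| Afterwards | Restart if resolved within 3 weeks | No restart |

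A related event that meets the trigger falls under both columns. An unrelated one falls under 6.1.4 and, going by the list heading, not under 6.1.3.

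**Step 3: is there a rule for choosing?**
- The lead-in to 6.1.3 names both outcomes but gives no test that sends this trigger to one or the other.
- 6.1.3 asks the investigator to contact the Protocol Chair. That is consultation, not a criterion.
- The 6.1.4 exceptions cover the named situations only, not the general trigger.
- Neither section adds a grade, a duration or a reversibility condition to the trigger.

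**Step 4: what depends on it.** Sections 1.1 and 10 schedule induction doses on days 1, 22, 43 and 64, and maintenance doses at weeks 24, 36, 48 and 60 for patients without progression at day 92: 4 + 4 = 8 doses. Take a related event that meets the trigger after dose 1.
- Under 6.1.4, none of the remaining 8 − 1 = 7 scheduled doses is given. The patient has one cycle and cannot meet the two-cycle requirement for response in Section 11.
- Under 6.1.3, if the event resolves in time, dose 2 can be given as late as day 22 + 21 = day 43. The two-cycle requirement can then be met, subject to the other Section 11 conditions (measurable disease at baseline, cells at the specified dose, disease re-evaluated).

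**Step 5: Section 5.6.** Read literally, an unacceptable adverse event that calls for only a temporary stop under 6.1.3 ends therapy. That does not fit 5.3.1, which permits delays, or 6.1.3, which says when to restart.

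**The case against.** The best defence is that both sections rest on investigator judgment in a single-center trial with the Protocol Chair consulted, so in practice one discussion settles each case. 6.1.3 also ends in removal from treatment when a delay runs too long, so the two sections might be read as a sequence: delay first, discontinue if the event does not resolve. Part of this stands, because consultation lowers the chance of inconsistent handling. It does not remove the conflict. Judgment decides whether the trigger is met; once it is met, 6.1.4 is mandatory and is not conditioned on failure to resolve.

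On 5.6 the defence is stronger. Its sentence opens by setting treatment delays aside, its bullet covers only unacceptable events, Section 5.2.2 lets patients proceed once immune events improve, and the off-therapy list in 5.7 has no temporary-stop criterion. The word temporary may well be loose drafting.

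A reader might infer more than the documents support, in four ways.
- **The two rules overlap completely.** They do not, because the 6.1.3 list is headed as related events. The heading is not applied cleanly (the list includes intercurrent illness, and a skin item that applies whatever the cause), but it is there.
- **There are three different outcomes.** The cells are given once, so stopping ipilimumab for good and ending therapy come to nearly the same thing. The real split is re-dosed or not.
- **Delay and restart preserves both DLT-window exposure and response evaluability.** A full 3-week delay puts dose 2 on day 43, after the 42-day DLT window, so exposure in the window is still one dose. DLT status is in any case set by Section 5.4.
- **Each such patient shifts any dose level 0 rate by 1/15, or 6.7 points, on 5 + 10 patients.** That holds only for a changed outcome over a fixed denominator. Leaving the response set changes the denominator, and 15 evaluable patients are not established. If 5 of 15 responded (an assumption), removing a non-responder gives 5/14 (35.7% against 33.3%, +2.4 points) and removing a responder gives 4/14 (28.6%, −4.8 points). PFS and OS run from the start of treatment, so neither rule drops a patient from them.

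**Conclusion.** The concern holds as an internal inconsistency and should be corrected. For treatment-related events, 6.1.3 and 6.1.4 prescribe incompatible mandatory actions for the same trigger, and nothing in the protocol chooses between them. The consequence for a patient is whether ipilimumab is given again: after the first dose, up to 7 of 8 scheduled doses. That count assumes timely resolution, no progression at day 92 and no other reason to stop. The consequence for analysis is confined to response evaluability when the event falls after the first dose. No bias in any rate can be computed, because the documents do not say how many patients will meet the trigger. The design is not invalidated. The 5.6 wording is a minor companion point, and the main finding stands without it.

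**What to change.** Reconcile 6.1.3 and 6.1.4 on this trigger in one of two ways: keep it in one list only, or keep it in both and state the feature that separates a delay from permanent discontinuation. Make the causality scope of the two sections explicit at the same time. Then align the 5.6 bullet, so that a temporary stop is described the same way there as in 5.3.1 and 6.1.3. Which clinical rule applies is for the sponsor to decide; the requirement here is only that the sections agree.

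The cost is a wording change to two sections and one bullet in the next amendment, with no added patients, visits or tests.

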6.1.5 Concomitant Treatments

Prohibited and/or Restricted Treatments

Subjects in this study may not have anti-tumor therapy (except hydroxyurea, with PI approval) for up to 4 weeks before and after dosing with Ipilimumab. Subjects must have not had immune suppression within 4 weeks of starting Ipilimumab. Patients started on systemic anti-neoplastic chemotherapy or immune suppression while on treatment will be taken off the study. The administration of live vaccinations while on treatment is prohibited. Short courses of corticosteroids for disease symptom control may be permitted after discussion with the Study Chair.

CONFIDENTIAL

This document is confidential. Do not disclose or use except as authorized.

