Ipilimumab will be administered intravenously over 90 ± 10 minutes after the DLI product observation period is completed, and dosing will continue in 3-week intervals for 4 cycles, unless unacceptable toxicity or symptomatic disease progression occurs (see Appendices E-F for disease progression criteria). MTD will be assessed at day 43 by DLT criteria as defined in **Section 5.4**. At their day 92 evaluation, patients without evidence of progressive disease or unacceptable toxicity can receive maintenance Ipilimumab **per their assigned dose level** on a q 3 monthly basis starting from week 24, for 4 doses.

5.1.5 Dose-escalation/De-escalation schema: Four dose-level combinations of CD25/Treg-depleted DLI plus Ipilimumab will be evaluated to determine MTD.

Table 4: CD25/Treg-depleted DLI plus Ipilimumab Dose Escalation/De-escalation Schema Per Cohort

Cohort	Viable CD3+ Dose (#cells/kg*)	Ipilimumab Dose
Dose Level +2	3×10^7	10 mg/kg
Dose Level +1	3×10^7	3 mg/kg
Dose Level 0	3×10^7	1 mg/kg
Dose Level -1	1×10^7	1 mg/kg

** Recipient's body weight in Kg

** Acceptable range: $0.8-1 \times 10^7$ viable CD3+ cells/kg for DL -1; $2.5-3 \times 10^7$ viable CD3+ cells/kg for DL 0, +1, and +2

To ensure at least 3 patients will be evaluable within a group, a cohort of 5 eligible patients will enter at each dose level. If there are fewer than 3 evaluable patients in a cohort, additional patients will be added at that dose-level. Patients may be enrolled in the next cohort when 3 or more evaluable patients from the previous cohort have completed their day 43 assessment. Patients will be considered unevaluable for the determination of MTD if they require removal from the study due to alternative treatments for progressive disease (except hydroxyurea, with PI approval) or other reasons not related to an adverse event within 6 weeks after initial dosing. Additional patients may be enrolled at a specific dose cohort to substitute for patients within the cohort who are considered unevaluable for MTD. **There will be at least one-week interval between consecutive enrollments at the same dose level during phase 1A.**

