5.2.2 Other Cycles

To proceed with subsequent cycles, subjects must not have:

- grade 2 or higher acute GVHD (see **Appendix C** for GVHD grading) requiring systemic immunosuppression
- extensive (or severe) chronic GVHD requiring systemic immunosuppression
- ongoing non-hematologic toxicity of grade 2 or higher unrelated to underlying malignancy or GVHD

Subjects will be allowed to proceed to subsequent cycles if they have ongoing:

- immune-related adverse events not defined as GVHD (e.g. diarrhea, pruritus, endocrinopathy, and rash) that have responded to corticosteroids and improve to grade 1 or less

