6.1.13 Monitoring and Management of Immune-mediated Adverse Reactions

We anticipate that Ipilimumab immune-mediate adverse reactions and GVHD will be difficult to distinguish clinically. No increase in GVHD was seen in the low dose, single-administration study of Ipilimumab in patients with hematologic malignancies post alloSCT. Therefore, for the present study, will need to use the experience with Ipilimumab in studies of solid tumor patients to guide us in distinguishing immune-related AEs from GVHD. Below is an overview of the approach to immune-related AEs utilized on prior Ipilimumab studies, which we will follow for the present study. In the present study, we will also encourage biopsy of the affected organ so that more can be learned about how to distinguish immunerelated AEs from GVHD pathologically.

Immune-mediated Enterocolitis

The clinical presentation of GI immune-related AEs included diarrhea, increase in the frequency of bowel movements, abdominal pain, or hematochezia, with or without fever. However inflammation may occur in any part of the GI tract including esophagitis and gastritis. Fatalities due to GI perforation have been reported in clinical trials of Ipilimumab. Patients should be carefully monitored for GI symptoms that may be indicative of immune-related colitis, diarrhea, or GI perforation. Diarrhea or colitis occurring after initiation of Ipilimumab therapy should be evaluated to exclude infectious or alternate etiologies.

In symptomatic patients, rule out infectious etiologies and consider endoscopic evaluation with biopsy to establish etiology and for persistent or severe symptoms. Withhold Ipilimumab dosing for any patients with enterocolitis pending evaluation; administer anti-diarrheal treatment and, if persistent evaluate with colonoscopy and biopsy (to distinguish GVHD vs. immune-mediated inflammation) and initiate systemic corticosteroids at a dose of 0.5 mg/kg/day prednisone or equivalent.

Permanently discontinue Ipilimumab in patients with severe enterocolitis and evaluate with colonoscopy and biopsy (to distinguish GVHD vs. immune-mediated inflammation), and initiate systemic corticosteroids at a dose of 1 to 2

CONFIDENTIAL

This document is confidential. Do not disclose or use except as authorized.

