This document is confidential. Do not disclose or use except as authorized.

Cardiac *	Management/Next Dose Ipilimumab Cardiac Toxicities
≤ Grade 1	Hold dose pending evaluation and observation.** Evaluate for signs and symptoms of CHF, ischemia, arrhythmia or myositis. Obtain history EKG, CK (for concomitant myositis), CK-MB. Repeat troponin, CK and EKG 2-3 days. If troponin and labs normalize may resume therapy. If labs worsen or symptoms develop then treat as below. Hold pending evaluation.
Grade ≥2 with suspected myocarditis	Hold dose.** Admit to hospital. Cardiology consult. Rule out MI and other causes of cardiac disease. Cardiac Monitoring. Cardiac Echo. Consider cardiac MRI and cardiac biopsy. Initiate high dose methylprednisolone. If no improvement within 24 hours, add either infliximab, ATG or tacrolimus. Resume therapy if there is a return to baseline and myocarditis is excluded or considered unlikely.
Grade ≥2 with confirmed myocarditis	Off protocol therapy. Admit to CCU (consider transfer to nearest Cardiac Transplant Unit). Treat as above. Consider high dose methylprednisolone. Add ATG or tacrolimus if no improvement. Off treatment.

*Including CHF, LV systolic dysfunction, Myocarditis, CPK, and troponin
 
**Patients with evidence of myositis without myocarditis may be treated according as “other event”
 
Note: The optimal treatment regimen for immune mediated myocarditis has not been established. Since this toxicity has caused patient deaths, an aggressive approach is recommended.
	

Overall, immune-related AEs commonly started within 3 to 10 weeks from first dose, were successfully managed in most instances by omitting doses, discontinuing dosing, and/or through administering symptomatic or immunosuppressive therapy, including corticosteroids, as detailed above. Immune-related AEs generally resolved within days to weeks in the majority of subjects.

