13.4 Determining MTD

Four escalating/de-escalating doses of the combination therapy will be considered to determine the MTD: CD25/Treg depleted DLI 3×10^7 CD3⁺ cells/kg + Ipilimumab 10 mg/kg (Dose level +2), CD25/Treg depleted DLI 3×10^7 CD3⁺ cells/kg + Ipilimumab 3 mg/kg (Dose level +1), CD25/Treg depleted DLI 3×10^7 CD3⁺ cells/kg + Ipilimumab 1 mg/kg (Dose level 0, starting level), and CD25/Treg depleted DLI 1×10^7 CD3⁺ cells/kg + Ipilimumab 1 mg/kg (Dose level -1). Considering the DLT observation period of 6 weeks and the accrual rate, the study will enroll 5 eligible patients at each dose level to minimize delays in accrual. Patients will be unevaluable for MTD if they receive DLI product with cells not meeting the dose-level criteria (**Section 5.1.3**), die of progressive disease without DLT, or have disease progression or other reason requiring removal from the study without DLT within the 6 week DLT observation period (**Section 5.4**).

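### Chronic GVHD to week 60 is not scheduled for patients who stop early; separately, 6.1.5 takes patients given steroids for immune-related events off study although 5.2.2 lets them continue

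*Combined protocol and SAP*

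**What the plan says.** **Chronic GVHD.** Section 1.3 lists the incidence and severity of chronic GVHD at about one year, fixed as week 60 after the cell infusion. Section 13.7 plans a cumulative incidence in which the only competing event is death before GVHD. It gives no censoring rule for patients who have left treatment. Table 6 places chronic GVHD assessments at screening, day 43 and day 92. Table 7 places them at weeks 24, 36, 48 and 60, for patients with stable disease or better at day 92 who go on to maintenance. The notes to the Supplemental Scheduling Table release patients who do not finish all eight cycles from the off-treatment visit. They ask for whatever standard-of-care appointments can supply, and keep toxicity recording open for three months from the final ipilimumab dose. Section 5.8 follows all patients for a year from the last study treatment for survival, disease status and other therapies; GVHD is not on that list. Section 5.1.7 follows patients who move to off-study therapy for survival, for one year from the DLI.

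**Steroids.** Under 6.1.5, patients started on "immune suppression while on treatment will be taken off the study". Its only steroid permission reads: "Short courses of corticosteroids for disease symptom control may be permitted after discussion with the Study Chair". For persistent enterocolitis, 6.1.13 tells investigators to "initiate systemic corticosteroids at a dose of 0.5 mg/kg/day prednisone or equivalent". Section 5.2.2 allows further cycles after immune-related events (irAEs) other than GVHD "that have responded to corticosteroids and improve to grade 1 or less". The note in 6.1.4 says "Ipilimumab may not be restarted while the subject is being treated with systemic corticosteroids".

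**Evaluability.** Section 13.4 makes patients unevaluable for MTD on disease progression or "other reason requiring removal from the study without DLT within the 6 week DLT observation period". Section 5.1.5 limits the second category to "other reasons not related to an adverse event within 6 weeks after initial dosing".

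**The concern.** A cumulative incidence needs each patient's status for as long as that patient is at risk. Here a patient who stops for progression or toxicity and stays alive is at risk to week 60, but nothing in the plan schedules anyone to look for chronic GVHD in that patient after day 92. Survival is tracked in the same patients, so the plan would capture the competing event more reliably than the event of interest. The patients affected are not a random subset: they include those stopped for irAEs or acute GVHD, whose later chronic GVHD risk may well differ from that of patients on maintenance. Severity is also at stake. A patient who stops because of chronic GVHD already counts as an event, but its later maximum severity is not followed.

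The 6.1.5 wording is a separate matter and does not cause this gap. Read literally, it ends study participation for patients whom other sections expect to keep treating. The 13.4 wording is a mismatch between two definitions of the same status.

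**Working it through.** **1. Calendar.** Inputs are the induction dose days 1, 22, 43 and 64 (1.1) and the maintenance weeks 24, 36, 48 and 60. Day = 7 × week + 1 gives 169, 253, 337 and 421, which matches the Supplemental Scheduling Table. Week 60 is therefore day 421.

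**2. From the last scheduled chronic GVHD assessment to day 421.**
- Last assessment at day 43: 421 − 43 = 378 days (90%).
- Last assessment at day 92: 421 − 92 = 329 days (78%).
- Last assessment at week 24, 36 or 48: 252, 168 or 84 days.

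**3. Allowing for toxicity recording.** Three months is taken as 90 days, the figure in 7.4.2. The 5.8 tracking is taken as 365 days from the last dose.

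| Last dose (day) | Toxicity recording ends (+90) | Days left to 421 | 5.8 tracking ends (+365) | Short of 421 by |
|---|---|---|---|---|
| 1 | 91 | 330 (78%) | 366 | 55 |
| 22 | 112 | 309 (73%) | 387 | 34 |
| 43 | 133 | 288 (68%) | 408 | 13 |
| 64 | 154 | 267 (63%) | 429 | 0 |
| 169 | 259 | 162 (38%) | 534 | 0 |
| 253 | 343 | 78 (19%) | 618 | 0 |
| 337 | 427 | 0 | 702 | 0 |

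Only a last dose at week 48 or later carries toxicity recording to week 60. Follow-up under 5.1.7 for patients on off-study therapy ends one year after the day 1 infusion, at day 366, also 55 days short.

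**4. What the analysis could do with such patients.** Section 13.7 leaves two routes. If they stay at risk until death or last known alive, any chronic GVHD that nobody recorded counts as none, and a later death counts as death without GVHD; the estimate is then too low. If they are censored at the last GVHD assessment, the estimate assumes that they would go on to develop chronic GVHD at the same rate as patients still on maintenance. The direction of error is then not fixed, but the assumption is doubtful.

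**5. Steroid provisions side by side.** Section 6.1.5 gives separate permission for short steroid courses for disease symptoms. That permission would be unnecessary if steroids fell outside its immune-suppression rule, so steroids are covered, and steroids for irAEs are not exempted. Against this stand 5.2.2 (continue once the event has responded), the 6.1.4 note (restart barred only during steroids, hence possible afterwards), and 5.4 item 4 (a non-neurologic irAE that responds to steroids and settles to grade 1 or less within 3 weeks is not a DLT). A patient who meets 5.2.2 after steroids is off study under 6.1.5 and eligible for the next cycle under 5.2.2.

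**6. Evaluability.** Consider a patient removed before day 43 because of an adverse event that is not a DLT. The patient is unevaluable under 13.4 but is not made so by 5.1.5. Section 5.1.7 agrees with 5.1.5, since it limits the exclusion to removal with no evidence of toxicity. The phase 1b rule in 13.4 compares a count of DLTs (at most 2, or 3 and more), and leaving out a patient without a DLT does not change that count.

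**The case against.** On chronic GVHD, the plan is not empty after day 92. Besides toxicity recording and standard-of-care data, Section 6 collects grade 3 and higher events up to the final study visit and allows later contact about unresolved toxicity. Section 5.8 also asks patients to accept long-term follow-up for late toxicities, with possible six-monthly calls to local providers. These matter, but none is a scheduled chronic GVHD assessment. The Section 6 collection misses lower grades and ends early for a patient with no further visit, and the long-term follow-up is optional and aimed beyond one year. It is also fair to say that the endpoint is secondary, that 13.7 is mainly descriptive, and that GVHD after off-protocol therapy is hard to attribute.

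On steroids, 5.2.2 speaks of immunosuppression for GVHD and of corticosteroids for irAEs, so 6.1.5 could be meant for GVHD-type treatment only. The sentence in 6.1.13 on "administering symptomatic or immunosuppressive therapy, including corticosteroids" summarises past experience and defines nothing for 6.1.5. Section 6.1.3 also allows restart after recovery, so several specific provisions point against one general sentence. For severe enterocolitis and grade 3 or higher hepatotoxicity, 6.1.13 stops ipilimumab permanently in any case. All of this stands as evidence of intent. It does not remove the conflict in the wording, but it shows that a short clause is enough.

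A reader might infer that the 13.4 wording distorts dose decisions or the reported DLT rate. The documents do not support that. Phase 1a is complete (13.4, June 2021 amendment), the phase 1b rule is a count, and no text ties the reported rate to the 13.4 set; Section 11 has its own definition of evaluable for toxicity.

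**Conclusion.** The chronic GVHD gap holds. As written, the plan gives selective ascertainment of a stated endpoint: after an induction stop, 267 to 330 of 421 days (63 to 78%) fall outside the toxicity window, and censoring there is plausibly informative. The day counts assume dosing on the scheduled days, 90 days for three months, and Table 7 as it can be read here. The informativeness is a judgement, not a calculation.

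How many patients are affected cannot be taken from the documents. A reader might subtract the prior DLI trial's 27% event-free survival from its 53% one-year survival (2.2.1) and apply the 26% to this trial, then treat all those patients as having unknown status. That trial gave no ipilimumab, the denominator of its 53% is not stated, and the step ignores the partial sources above. It would be a worst-case bound, not an estimate of impact.

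The 6.1.5 rule is wrong as written, because it conflicts with 5.2.2, 5.4 item 4 and the 6.1.4 note. The 13.4 mismatch is a matter of alignment only. Nothing here changes a dose decision or the primary conclusion.

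**What to change.** 1. **Section 5.8:** add acute and chronic GVHD status (onset date and maximum severity) to the existing tracking for all patients, including early stoppers and those on off-study therapy under 5.1.7. Continue it through at least week 60 after cell infusion. The information can come from records or local providers, without extra visits. The cost is slightly more data collection and at most 55 more days of tracking per patient.
2. **Section 6.1.5:** replace removal from the study with removal from protocol treatment, and exempt corticosteroids given for non-GVHD irAEs that meet 5.2.2. The cost is one clause.
3. **Section 13.4:** carry over the limit in 5.1.5, so that the residual category covers only "other reasons not related to an adverse event within 6 weeks after initial dosing". This is a wording change for consistency, with no effect claimed on dose decisions.
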